Observed rate of exit site infections in the C-Pulse® clinical study was 40%. However the risks associated with this type of infection are low. Normally the resolution of this type of infection is managed through use of antibiotics, antiseptics, exit site management and PIL stabilization. Since C-Pulse® is not blood contacting, the risk of sequelae, particularly sepsis, is significantly less than observed with LVADs, thus exit site infections with the C-Pulse® device are not as high a risk as in LVADs. There remains a risk of ascending infection – exit-site pain, tenderness or swelling over the subcutaneous flocking, etc., should be investigated and treated aggressively. The PIL is specifically designed as a modular component of the C-Pulse® System, such that if an infection is chronic the PIL can be removed and the infection easily treated with antibiotics.

Adoption of the requirement for a stabilization device and new infection management techniques and protocol will require the sites to treat the C-Pulse® PIL as critically as the VAD drivelines to facilitate minimizing infection. The anticipated rate of residual risk in the post-market experience following implementation of the mitigations is expected to be no greater

than 30%. This rate is acceptable since it is consistent with what is currently being experienced with other devices having a drive-line exit site.

The clinical benefit of the PIL and its design features (e.g. ease of accessibility, ability for the patient to temporarily disconnect, removability) continue to support that the benefit outweighs the residual risk.

2) Sternal wound infection

During the C-Pulse® clinical study, one patient experienced a sternal wound infection resulting from the surgical procedure. The outcome of the management of the sternal wound after several attempts for debridement and a sternal flap was an aortic disruption. The rate of this incident is low, observed at 5% (1/20).

The risks associated with this type of infection are high if not properly managed. Resolution of this type of infection is normally managed through use of antibiotics and sternal wound debridement and drainage. If the sternal wound infection progresses to include the sternal bone the Cuff should be explanted to avoid infection of the Device.

3) Pneumo-mediastinum Infection

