- 1) **Pump** failure (implanted components of pump and any motor or other pump actuating mechanism that is housed with the implanted components). In the special situation of **pump thrombosis**, thrombus is documented to be present within the device or its conduits that result in or could potentially induce circulatory failure.

Note: For C-Pulse system – this includes the Cuff and Gas line and/or ECG lead.

- 2) **Non-pump** failure (e.g., external pneumatic drive unit, electric power supply unit, batteries, controller, interconnect cable, compliance chamber).

Note: For C-Pulse system – this includes the Percutaneous Interface Lead and the Driver.

Hemolysis

A plasma-free hemoglobin value that is greater than 40 mg/dl, in association with clinical signs associated with hemolysis (e.g., anemia, low hematocrit, hyperbilirubinemia) occurring after the first 72 hours post-implant. Hemolysis related to documented non-device-related causes (e.g. transfusion or drug) is excluded from this definition.

Hepatic Dysfunction

An increase in any two of the following hepatic laboratory values (total bilirubin, aspartate aminotransferase/AST and alanine aminotransferase/ALT) to a level greater than three times the upper limit of normal for the hospital, beyond 14 days post-implant (or if hepatic dysfunction is the primary cause of death).

Hypertension

New onset blood pressure elevation greater than or equal to 140 mm Hg systolic or 90mmHg diastolic (pulsatile pump) or 110mmHg mean pressure (rotary pump).

Major Infection

A clinical infection accompanied by pain, fever, drainage and/or leukocytosis that is treated by anti-microbial agents (non-prophylactic). A positive culture from the infected site or organ should be present unless strong clinical evidence indicates the

need for treatment despite negative cultures. The general categories of infection are listed below:

Localized Non-Device Infection

Infection localized to any organ system or region without evidence of systemic involvement (see sepsis definition), ascertained by standard clinical methods and either associated with evidence of bacterial, viral, fungal or protozoal infection, and/or requiring empirical treatment.

Percutaneous Site and/or Pocket Infection (PIL Only)

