A positive culture from the skin and/or tissue surrounding the drive line or from the tissue surrounding the external housing of a pump implanted within the body, coupled with the need to treat with antimicrobial therapy, when there is clinical evidence of infection such as pain, fever, drainage or leukocytosis.

Internal Pump Component, Inflow or Outflow Tract Infection (Cuff, ECG Lead and Gas line not including the PIL)

Infection of the implanted C-Pulse Cuff or surrounding tissue (e.g. aorta) documented by positive site culture.

Sepsis

Evidence of systemic involvement by infection, manifested by positive blood cultures and/or hypotension.

Myocardial Infarction

Two categories of myocardial infarction will be identified:

Peri-Operative Myocardial Infarction

The clinical suspicion of myocardial infarction together with CK-MB or Troponin > 10 times the local hospital upper limits of normal, found within 7 days following implant together with ECG findings consistent with acute myocardial infarction.

Non-Perioperative Myocardial Infarction

The presence at > 7 days post-implant of two of the following three criteria:

- a) chest pain which is characteristic of myocardial ischemia,
- b) ECG with a pattern or changes consistent with a myocardial infarction, and
- c) Troponin or CK (measured by standard clinical pathology/laboratory medicine methods) greater than the normal range for the local hospital with positive MB fraction ($\geq 3\%$ total CK). This should be accompanied by a new regional LV or RV wall motion abnormality on a myocardial imaging study.

Neurological Dysfunction

Any new, temporary or permanent, focal or global neurological deficit ascertained by a standard neurological examination (administered by a neurologist or other qualified physician and documented with appropriate diagnostic tests and consultation note). The examining physician will distinguish between a transient ischemic attack (TIA), which is fully reversible within 24 hours (and without evidence of infarction), and a stroke, which lasts longer than 24 hours (or less than 24 hours if there is evidence of infarction). The NIH Stroke Scale (for patients > 5 years old) must be re-administered at 30 and 60 days following the event to document the presence and severity of neurological deficits. Each neurological event must be subcategorized as:

- 1) Transient Ischemic Attack (acute event that resolves completely within 24 hours with no evidence of infarction)

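### Section 8.2.4 demands a positive culture for exit-site and internal infections although its parent definition accepts culture-negative cases, so the named infection endpoints can be undercounted

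*Combined protocol and SAP*

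**What the plan says.** Four definitions in Section 8.2.4 matter here.

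- **Major Infection (parent).** It needs clinical signs and non-prophylactic antimicrobial treatment. On culture it says "A positive culture from the infected site or organ should be present unless strong clinical evidence indicates the" and continues "need for treatment despite negative cultures. The general categories of infection are listed below".
- **Percutaneous Site and/or Pocket Infection (PIL Only).** It starts from "A positive culture from the skin and/or tissue surrounding the drive line" (or from around an implanted housing), "coupled with the need to treat with antimicrobial therapy, when there is clinical evidence of infection such as pain, fever, drainage or leukocytosis". No exception is given.
- **Internal component infection.** It must be documented by a positive site culture. Its heading lists the cuff, ECG lead and gas line, and leaves the PIL out.
- **Localized Non-Device Infection.** It covers any organ system or region without systemic involvement, "either associated with evidence of bacterial, viral, fungal or protozoal infection, and/or requiring empirical treatment".

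Section 6.4 names exit-site infection and internal PIL/cuff infection among the primary safety endpoints, next to a general entry for all protocol-defined adverse events. Section 4.3 reports a 40% exit-site infection rate in the premarket study and says the post-market rate "following implementation of the mitigations is expected to be no greater" than 30%.

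**The concern.** The parent and its device sub-categories apply different culture rules, and no section says where a treated, culture-negative driveline or cuff infection belongs. The only localized category whose text would admit it is the one titled Non-Device.

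The stakes are specific to this device. Section 4.3 identifies infection as one of two main risk areas and calls the expected residual exit-site rate acceptable. Section 4.1 says the study is to confirm the premarket results, and Section 6.5 foresees pooling and comparison with the US trial. All of these need one stable case definition. If the culture rule removes cases from the endpoint, a lower rate may reflect the definition and not fewer infections. Two sites could also classify the same event differently.

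**Working it through.** **Step 1: place one case.** Take an exit-site infection with drainage, treated with antimicrobials, with a negative culture.

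| Definition in 8.2.4 | Positive culture | Admits the case? |
|---|---|---|
| Major Infection | Expected, with an exception | Yes |
| Percutaneous Site/Pocket (PIL) | Required | No |
| Internal component | Required | No, and the PIL is left out |
| Localized Non-Device | Not required | By its text yes, by its title no |
| Sepsis | Blood culture and/or hypotension | Only with systemic involvement |

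The case is a Major Infection with no device category. A treated, culture-negative cuff infection ends in the same place. A case in which no culture was taken is placed even less clearly, because the parent exception speaks of negative cultures.

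**Step 2: direction.** Let p be the true rate of clinically evident, treated exit-site infection whatever the culture result, and c the share of those that are culture-negative. Under the literal rule:

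counted rate = p × (1 − c)

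Since c cannot be negative, the counted rate cannot exceed p.

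**Step 3: size, as an illustration.** Inputs: N = 50 (Section 6.6) and p = 40%, the premarket rate in Section 4.3 taken as unchanged. The documents give no value for c, so 0 to 40% is assumed. Intervals are exact (Clopper-Pearson) 95%. The last column is the binomial chance of counting 15 or fewer of 50, that is, 30% or less.

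| c (assumed) | Counted rate | Count of 50 | 95% CI | P(15 or fewer) |
|---|---|---|---|---|
| 0 | 40% | 20 | 26.4% to 54.8% | 0.10 |
| 10% | 0.40 × 0.90 = 36% | 18 | 22.9% to 50.8% | 0.23 |
| 20% | 0.40 × 0.80 = 32% | 16 | 19.5% to 46.7% | 0.45 |
| 25% | 0.40 × 0.75 = 30% | 15 | 17.9% to 44.6% | 0.57 |
| 40% | 0.40 × 0.60 = 24% | 12 | 13.1% to 38.2% | 0.88 |

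At c = 25% the count equals the Section 4.3 expectation with no real change. That value is simply the one that turns 40% into 30%; nothing in the documents points to it.

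**Step 4: the premarket figure.** Section 4.3 gives another event as 5% (1/20). If the same denominator applies, 40% is 8/20, with exact 95% CI 19.1% to 63.9%. The culture rule behind the 40% is not stated. If it already required a positive culture, the all-treated premarket rate would have been 0.40 / (1 − c), for example 0.40 / 0.75 = 53% at c = 25%. A culture-confirmed post-market rate would then be like for like with the 40% if c is the same in both studies, and an all-treated rate would not be.

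**The case against.** The case on the other side has several parts.

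- **The exception may carry down.** The categories are introduced directly after the culture exception, as divisions of Major Infection, so an investigator could apply it to all of them. This reading is possible, but the text does not state it. The PIL category sets out its own cumulative conditions.
- **The Non-Device title excludes driveline cases.** This is a fair reading. A reader might infer that such infections will in fact be counted as non-device; the documents do not establish that. If the title governs, however, the case has no localized category at all and the endpoint still loses it.
- **Nothing goes unreported.** This stands. The case meets Major Infection and falls under the endpoint for all protocol-defined adverse events. Relation to treatment is to be summarised (Section 6.5), and an event related to device use is an adverse device effect whatever its sub-category (Section 8.2.2). The loss is from the named endpoints only.
- **The 30% is not a target.** This also stands. A reader might infer a commitment that an undercount would falsely satisfy. Section 4.3 states an expectation within the risk rationale, adverse events are summarised descriptively (Section 6.5), and no rule declares success at 15/50. The interval for 15/50 includes 40% in any case.
- **The wording follows a registry.** Section 8.2.4 says so, but the protocol already departs from it for major bleeding and adds two definitions of its own. Keeping the registry rate does not prevent reporting a second one.
- **The link from endpoint to category is inferred.** True. No section makes it, and the internal endpoint names the PIL while the internal category leaves it out. This is part of what needs correcting.

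**Conclusion.** The inconsistency is on the page. Applied literally, Section 8.2.4 can only lower the named exit-site and internal infection rates relative to all clinically evident, treated infections at those sites. The conclusion assumes that the sub-category wording governs and that the Section 6.4 endpoints correspond to those categories, which is the closest match the protocol offers.

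The size is unknown. The range of 36% to 24% rests on an assumed culture-negative share of 10% to 40% and on an unchanged true rate of 40% that counts culture-negative cases. If the premarket 40% already required a positive culture, the distortion in the comparison disappears when the culture-negative share is the same in both studies, although the total burden is still understated. A reader might also infer that culture practice differs between sites. Section 5.6 says only that assessments follow routine practice and does not address cultures.

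This is a cheap improvement to an endpoint definition. It does not show that infections will go unreported or that the study's conclusions are invalid.

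**What to change.** 1. Map the Section 6.4 endpoints for exit-site infection and internal PIL/cuff infection explicitly to the Section 8.2.4 categories, and reconcile the internal endpoint, which names the PIL, with the internal category, which leaves it out.
2. State that infections at PIL, cuff, gas-line and ECG-lead sites are not classified as Localized Non-Device Infection.
3. Record culture status for each infection at these sites: positive, negative or not done.
4. Report two rates for each endpoint: culture-confirmed (the registry definition), and all clinically evident, antimicrobial-treated infections at those sites.
5. State the definition that produced the premarket 40%, and compare with the 40% and 30% figures only on that definition.

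The cost is one e-CRF field, one additional table row and a possibly higher reported rate. Patient care does not change, because the field records whether a culture was taken and does not require one.

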8.3. Deaths and Explants

8.3.1. . Subject Deaths

In the event of subject death, every effort should be made to obtain a copy of the autopsy report and/or death summary. Information on the cause of death and its relationship to the device used in this clinical investigation will be determined by the principal investigator. Copies of an autopsy report, if available, and/or a death summary are to be sent to the Investigation Sponsor.

If a device is explanted during autopsy, the device should be returned to the Investigation Sponsor for analysis. Return kits for devices will be provided upon request by the clinical monitor.

8.3.2. . Device Explants

In the event a device component is explanted in the intra-operative or early post-operative period (i.e., while the patient is hospitalized at the investigational center), a copy of the procedure report must be provided to the Investigation Sponsor. Information on the cause of explant and its relationship to the device component will be determined by the principal investigator. Explanted device components during this period must be returned to the Investigation Sponsor for analysis. Return kits for devices will be provided upon request by the clinical monitor.

In the event a device component is explanted in the late post-operative period, every effort should be made to obtain a copy of the explant procedure report, as applicable. Information on the cause of explant and its relationship to the device component will be

determined by the principal investigator. Copies of an explant report, if available, are to be sent to the Investigation Sponsor. Explanted device components during this period should be returned to the Investigation Sponsor for analysis. Return kits for devices will be provided upon request by the clinical monitor.

9. STUDY CONDUCT, RESPONSIBILITIES AND CONFIDENTIALITY

The study will be conducted in accordance with Good Clinical Practice (GCPs) and the Declaration of Helsinki and any additional provisions outlined in the Study Agreement.

The study physicians are responsible for obtaining the appropriate regulatory approvals (ethics committee and/or competent authority) prior to initiation of the study. The Investigator will provide current copies of the study protocol to all Co-Investigators or other staff responsible for study conduct.

9.1. Patient Authorization

Patient authorization and written informed consent must be obtained prior to the patient's enrollment into the study and in accordance with GCPs, the Medical Devices Directive and all other applicable standards, regulations (local and national), guidelines and institutional policies.

9.2. Patient Confidentiality

Patient confidentiality must be maintained in accordance with GCPs, the Medical Devices Directive and all other applicable standards, regulations (local and national), guidelines and institutional policies.

9.3. Physician Confidentiality

Study physicians will comply with the applicable provisions of the study agreement with regard to nondisclosure and confidentiality.

9.4. Device Accountability

The Investigator shall document in the surgery reports and e-CRFs the serial/lot number of all devices used during procedures.

9.5. Protocol Changes/Amendments

Protocol changes or amendments cannot be made by the study physician without prior written approval by the Sponsor and EC.

9.6. Patient Termination or Withdrawal

Once enrolled, patients may discontinue participation at any time by withdrawing informed consent or meeting the requirement for termination. Participation in the study is entirely voluntary.

10. PUBLICATION POLICY

All information related to the study device is considered confidential and remains the sole property of the Sponsor. This includes, but is not limited to the patent applications and the manufacturing process. The investigator agrees to use this information only to accomplish this study and will not use it for other purposes without the Sponsor's written consent. The investigator understands that the information developed in the clinical study will be used by the Sponsor and may be disclosed as required to other investigators or competent authorities. To permit the information derived from the clinical studies to be used, the investigator is obliged to provide Sponsor (or designated representative) all data obtained in the study.

Sponsor and investigators are committed to the publication and widespread dissemination of the Study results. This study represents a joint effort between sponsor and investigators, and as such, the parties agree that the recommendation of any party concerning manuscripts or text shall be taken into consideration in the preparation of final scientific documents for publication or presentation.

At various milestones in the C-Pulse System study, including the conclusion, it is intended that multicenter papers will be published, in peer reviewed scientific journals and scientific meetings. These publications/presentations will be coordinated by Sunshine Heart via the Investigator Meeting. Publication (abstracts and manuscripts) or presentation of the study results are subject to review by Sunshine Heart prior to submission or presentation. Sunshine Heart will review the manuscript within sixty (60) days after receipt with the purpose to ensure technical accuracy of the information presented. If any such proposed publication or presentation contains patentable subject matter which in Sponsor's sole discretion, warrants intellectual proprietary protection, the sponsor may delay any publication or presentation for up to 1 month after sponsor approval for the purpose of pursuing such protection.

Authors of publications will include the participating physicians who have enrolled significant numbers of patients. Final author lists will be based on direct involvement in hypothesis generation, data analysis, patient recruitment, and composition of abstracts and manuscripts. The final decision about author lists will be the prerogative of the sponsor and the participating Investigators in accordance with guidelines to authors for each journal.

If a multicenter publication is not issued after 1 year from the conclusion of the C-Pulse System Study (final database closure), single center results may be published with review by Sunshine Heart within 30 days of submission. Exceptions to this rule require prior approval from Sunshine Heart.

